10.2 Planned analyses

The primary outcomes will be CSF and plasma LZD PK parameters, including CSF to plasma ratio, rate of CSF uptake, and plasma absorption rate constant (k_a), drug clearance (Cl/F), volume of distribution (V_d). We will employ a model-based approach using non-linear mixed effects modeling in NONMEM to estimate plasma and CSF PK parameters based on simultaneous analysis of all plasma and CSF drug concentration data.⁷⁴ We will perform post-hoc Bayesian predictions of secondary LZD PK parameters, including C_{max} , time to C_{max} , AUC₀₋₂₄, and elimination half-life in plasma and in CSF. Based on this approach, we will characterize the dynamic uptake of LZD in the CSF when administered with high and standard dose RIF over 4 weeks and derive a dosing algorithm for LZD to achieve target exposures through simulations. Pharmacodynamic breakpoints for LZD against TB are not established, but we will use target AUC₀₋₂₄, AUC/MIC, T>MIC for LZD of 160 µg*hr/mL, 100, and 85%, respectively.^{23,75,76} We will use sparse sampling to estimate the AUC curve based on CSF sampling early, at steady state, and before LZD discontinuation.⁷⁷

For the LZD adverse event evaluation, the primary outcome will be a dichotomous measure of Grade 3 or higher (yes/no) myelosuppression (e.g., anemia, thrombocytopenia, leukopenia) during the 4 weeks of therapy. A secondary outcome will be LZD discontinuation or dose reduction (yes/no) for any AE. We will compare the frequency of myelosuppression between the LZD and no LZD arms across RIF dosing with the Cochran-Mantel-Haenszel test, which accounts for stratified randomization. Within

the LZD arm, we will explore differences in the frequency of myelosuppression between the standard and two high dose RIF arms combined by a chi-square test. We will use an exposure-response model using logistic regression to test if the probability of myelosuppression and LZD discontinuation is related to PK measurements, including C_{min} , C_{max} and AUC₀₋₂₄.

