- **DESIGN** ALTER is a phase II randomized, open-label trial using a factorial design of high or standard dose rifampicin with or without linezolid for the first 4 weeks of treatment for tuberculous meningitis (TBM). Initial randomization will be to high (35 mg/kg/day) versus standard (10 mg/kg/day) dose oral rifampicin for 4 weeks. After randomization to high versus standard dose rifampicin, participants will undergo a second randomization to linezolid 1200 mg daily versus no linezolid for 4 weeks.
- DURATION 24 weeks
- SAMPLE SIZE 60 participants
- **POPULATION** Participants with definite, probable, or possible TBM, aged \geq 18 years
- SETTING Masaka Regional Referral Hospital, Masaka, Uganda
- **STRATIFICATION** Participants will be randomized with stratification by HIV status and stage of disease (Grade 1 vs. 2 and 3), as defined by the modified British Medical Research Council criteria.
- **REGIMEN** Participants will first be randomized 1:1 to:

High dose rifampicin 35 mg/kg for 4 weeks vs. standard dose rifampicin 10 mg/kg

Participants will then be randomized 1:1 to:

Linezolid 1200 mg daily for 4 weeks vs. no linezolid (see **Table 1**)

In addition, all participants will receive standard treatment for TBM with isoniazid 5 mg/kg/day, pyrazinamide 25 mg/kg/day, ethambutol 20 mg/kg/day, corticosteroids (IV dexamethasone 0.4 mg/kg/day for 1 week, 0.3 mg/kg/day for 1 week, followed by a prednisone taper over 6 weeks), and vitamin B₆ 50 mg daily. After the first 4 weeks of therapy, participants in the high dose rifampicin arm (Arm A) will receive standard dose oral rifampicin (10 mg/kg/day) for another 11 months as per national guidelines.

		RI	F
colid		High dose (35 mg/kg)	Standard dose (10 mg/kg)
inez	+	Arm A: R ₃₅ HZEL	Arm B: R ₁₀ HZEL
	-	Arm C: R ₃₅ HZE	Arm D: R ₁₀ HZE

 Table 1: Study regimens

R, rifampicin; H, isoniazid; Z, pyrazinamide; E, ethambutol; L, linezolid

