2.0 HYPOTHESIS

CSF and plasma LZD PK exposure parameters will be lower when administered with high dose compared with standard dose RIF.

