4.0 STUDY DESIGN

This is an open-label, randomized clinical trial with a factorial design. Initial randomization will be to high (35 mg/kg/day) versus standard (10 mg/kg/day) dose oral rifampin for the first 4 weeks of intensive therapy. Participants will then undergo a second randomization to linezolid 1200 mg daily versus no linezolid for the first 4 weeks of therapy. We will use a computer generated permuted block randomization (block size = 2 or 4) stratified by TBM grade (1 vs 2 and 3), given the association between TBM severity and mortality. The trial is open label, although we will endeavor for research staff assessing adverse events, neurocognitive and functional outcomes, and PK data to be blinded.

Initiation of high or standard dose oral rifampicin and linezolid or no linezolid will begin immediately (within 24 hours) after randomization. In addition, all participants will receive a standard backbone of oral TB treatment with INH 5 mg/kg/day, PZA 25 mg/kg/day, EMB 20 mg/kg/day, corticosteroids (IV dexamethasone 0.4 mg/kg/day for week 1, 0.3 mg/kg/day for week 2, followed by a prednisone taper over 6 weeks), and vitamin B₆ 50 mg daily. After the first 4 weeks of therapy, participants will receive standard dose oral RIF (10 mg/kg/day) for another 11 months along with standard treatment for TBM per national guidelines. Patients admitted to Masaka Regional Referral Hospital who meet eligibility criteria will be invited to participate.

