4.1.7 Randomization

At study entry and prior to the 4th dose of TB treatment, participants will first be randomized by a computer-generated permutated block randomization (block size of 2 or 4) with a 1:1 randomization to high (35 mg/kg) versus standard dose (10 mg/kg) rifampicin. A second 1:1 randomization will then be performed to linezolid 1200 mg daily or no linezolid. Randomization will be stratified by British Medical Research Council (BMRC) TBM disease grade (Table 2), determined at the time of consent, given the association between worse disease severity and higher mortality¹.

Table 2. British Medical Research Council (BMRC) TBM disease grade

GRADE I	Glasgow coma score 15, no focal neurological signs
GRADE II	Glasgow coma score 11–14 with or without focal neurological sign or Glasgow coma score 15 with focal neurological signs
GRADE III	Glasgow coma score \leq 10 with or without focal neurological signs

The randomization schedules will be provided to the site pharmacy in a listed sequence. The sequential, unique randomization code will be recorded on the study entry CRF to assure there is no

skipping of the randomization order. All randomized participants will initiate their allocated study TB treatment within 24 hours of randomization and ideally the same day. For participants from whom informed consent has been obtained, but who are deemed ineligible or who do not enroll into the protocol, a Screening Failure form must be completed and entered into the database.

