10.0 STATISTICAL CONSIDERATIONS

10.1 Sample size estimation

Sample size calculations for the PK analyses are based on different study designs (varying number of participants and time points) using clinical trial simulations. We used the stochastic simulationestimate "sse" methodology for clinical trial simulation and re-estimation to determine sample sizes required to evaluate key PK parameters with precision adequate to determine optimal dosing for a future efficacy trial of LZD. This methodology simulates the data from a planned trial with a proposed design (e.g., number of participants) followed by the estimation of the parameters under the true and alternative models. This is repeated a minimum of 1000 times to estimate PK parameters, standard errors and inter-individual variability. With 30 participants receiving LZD, we will be able to estimate PK parameters with required precision of relative standard errors <10% for typical values and <25% for random effects (inter-individual variability). For the evaluation of LZD adverse events, if we assume 40% of participants in the LZD arm and 10% in the no LZD arm will experience myelosuppression.^{78,84} the planned sample size of 60 participants (n=30 per arm) will provide at least 80% power to detect a similar or greater difference in the frequency of myelosuppression between arms at a significance level of 0.05. Given the modest sample size, we recognize that we may not have adequate power to compare the frequency of myelosuppression in participants on LZD and standard versus high dose RIF; however, if the frequency of myelosuppression in participants on LZD and high dose RIF (n=20) is anticipated as \sim 25%, the 90% confidence interval of this estimate is 10% to 46% with a precision of 18%.

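### Section 10.1 counts 20 participants on linezolid plus high-dose rifampicin and 10.2 gives them two arms, but the 2x2 design has one such arm of about 15; the CMH strata are also not clearly named

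*Combined protocol and SAP*

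**What the plan says.** **Design.** The synopsis and 4.1.7 plan 60 participants, randomised 1:1 to RIF dose. Then "A second 1:1 randomization will then be performed to linezolid 1200 mg daily or no linezolid". Table 1 shows four arms. Only Arm A combines LZD with high-dose RIF; Arm B is LZD with standard RIF, and Arms C and D have no LZD. Section 3.3 replaces late exclusions to keep the arms balanced.

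**Section 10.1.** It plans 30 participants on LZD and 30 not. It then says that the myelosuppression rate in "participants on LZD and high dose RIF (n=20) is anticipated as" about 25%, and that "the 90% confidence interval of this estimate is 10% to 46% with a precision of 18" per cent.

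**Section 10.2.** Myelosuppression is compared "between the LZD and no LZD arms across RIF dosing with the Cochran-Mantel-Haenszel test, which accounts for stratified randomization". Within LZD, an exploratory chi-square test sets standard-dose RIF against two high-dose RIF arms taken together.

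**Stratification.**
- Synopsis: "Participants will be randomized with stratification by HIV status and stage of disease (Grade 1 vs. 2 and 3").
- Section 4.0: "stratified by TBM grade (1 vs 2 and 3), given the association between TBM severity and mortality".
- Section 4.1.7: "Randomization will be stratified by British Medical Research Council (BMRC) TBM disease grade (Table 2), determined at the time of consent".

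**The concern.** The precision statement in 10.1 rests on a group size that the design does not plan for, and the exploratory test in 10.2 names an arm that does not exist. The two statements fit each other: 30 LZD recipients in three arms of 10, two of them high-dose, would give 20. They do not fit Table 1. An analyst who follows 10.2 literally cannot tell which participants to compare.

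The CMH sentence has a related, lesser weakness. It claims to respect the stratified randomisation, but the only variable it mentions is RIF dose. That is the other randomised factor, and no section lists it as a stratification factor. The listed factors are grade alone (4.0, 4.1.7) or grade with HIV status (synopsis).

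Myelosuppression is the lead outcome of the LZD adverse-event evaluation and the only comparison with a power calculation. In an open-label trial its strata and groups are better fixed in advance.

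**Working it through.** **1. Size of the LZD plus high-dose RIF arm.** Inputs: 60 participants and two 1:1 allocations (synopsis, 4.1.7).
- 60 × 1/2 × 1/2 = 15, or from the 30 LZD recipients in 10.1, 30 × 1/2 = 15.
- Counting all high-dose participants does not give 20 either: Arms A + C = 15 + 15 = 30.
- In simulated randomisations stratified by grade (permuted blocks of 2 or 4), Arm A averaged 15.0. It ranged from 13 to 17 if LZD is blocked within RIF dose. If it is not, the 5th to 95th percentiles were 11 to 19, and 20 or more occurred in 2.2% of trials.

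**2. The plan's interval, then the same interval at n=15.** Exact (Clopper-Pearson) 90% limits for x events in n: lower = Beta quantile at 0.05 with parameters (x, n−x+1); upper = Beta quantile at 0.95 with parameters (x+1, n−x). The half-width is (upper − lower)/2.

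| Events / n | Rate | 90% interval | Half-width (points) |
|---|---|---|---|
| 5/20 (plan) | 25% | 10.4% to 45.6% | 17.6 |
| 3/15 | 20% | 5.7% to 44.0% | 19.1 |
| 3.75/15 (interpolated) | 25% | 8.6% to 49.3% | 20.4 |
| 4/15 | 26.7% | 9.7% to 51.1% | 20.7 |

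The first row reproduces the stated 10% to 46% and 18%; the Wilson interval (12.7% to 43.2%) and the Wald interval (9.1% to 40.9%) do not. So the method and arithmetic are sound and only the n is wrong. Like for like at 25%, the half-width rises by 20.4 − 17.6 = 2.8 points.

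**3. The 80% power for LZD against no LZD.** Inputs from 10.1: 40% against 10%, 30 per arm, alpha 0.05 (two-sided assumed, because 10.1 does not say). Results: arcsine 80.3%, unpooled normal 81.6%, exact enumeration of the uncorrected chi-square 79.6%, pooled normal 78.0%. The claim is reproduced to within about 2 points, and none of these calculations uses n=20.

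**4. Effect of the CMH strata.** These are simulated trials of 60 (10,000 to 20,000 per setting), randomised by grade, with CMH lacking a continuity correction. The share with grade 2–3 (60% here) and the odds ratio (OR) of grade for myelosuppression are assumptions. Cells show power in %, RIF dose alone / RIF dose by grade.

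| Setting | OR 1 | OR 2 | OR 6 |
|---|---|---|---|
| LZD blocked within RIF, 40% v 10% | 79.3 / 79.2 | 79.7 / 80.3 | 80.0 / 82.8 |
| LZD not blocked within RIF, 40% v 10% | 78.4 / 77.4 | 79.2 / 78.9 | 79.5 / 81.5 |

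These, together with runs at 40% and 80% grade 2–3 and runs in which the LZD rate differs by RIF dose, give changes from adding grade of −1.3 to 0.0 points at OR 1, −0.8 to +0.6 at OR 2 and +0.7 to +3.5 at OR 6. Type I error with 10% in both arms was 4.0–5.2% (RIF alone) and 4.4–5.1% (RIF by grade).

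**The case against.** **The CMH sentence is ambiguous.** It never calls RIF dose the stratum. It can be read as pooling LZD over RIF dose, the factorial margin, and stratifying the test by the randomisation factors. On that reading its claim holds. This objection stands. A reader might infer that the test omits grade and that the stated property is false, but the text does not establish that. RIF dose could also be a stratum in effect, if the second allocation is blocked within RIF arm; 4.1.7 does not say. What survives is that the strata are not clearly named and that the listed factors conflict on HIV status.

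**Grade may not matter for this outcome.** Sections 4.0 and 4.1.7 justify it by mortality, and nothing in the documents ties it to myelosuppression. OR 1 is then a reasonable default, and adding grade gains nothing. That stands too. A continuity correction, which 10.2 does not mention, would move power far more: with RIF dose as strata, from 79.8% to 69.4%.

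**The loss of precision is small.** A reader might set the 51% upper limit from 4/15 against the plan's 46%, but that changes the event rate as well as n; 3/15 gives 44.0%. Section 10.1 already concedes low power for the RIF comparison within LZD, and 10.2 only explores it. This limits the consequence but does not make n=20 or the second arm correct.

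**Could Arm A reach 20?** Replacement of late exclusions could raise the number randomised, but five extra in one arm would be needed, and 10.1 plans on 60 and 30.

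**Conclusion.** The n=20 in 10.1 and the two high-dose arms in 10.2 are wrong as written. The design has one LZD plus high-dose RIF arm, Arm A, of about 15. The precision at 25% is about 20 points rather than 18, with an interval of about 9% to 49%. The 15 is derived from the allocation ratios; the documents do not state it, and the realised count may differ.

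The CMH point is minor: the strata need naming, and the synopsis needs reconciling with 4.0 and 4.1.7 on HIV status. Its size rests on assumed grade prevalence and prognostic strength.

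A reader might infer from the misfit that the trial was sized for a different layout. The documents do not support that: the total of 60 and the 30 per LZD arm agree with the 2x2 design, and neither the power claim nor the PK precision claim uses n=20. Type I error stays near 5%. The effect is confined to a secondary safety evaluation.

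**What to change.** - **Section 10.1:** replace n=20 with about 15, and restate the exact 90% interval as about 9% to 49% with precision of about 20 points at 25%. Giving the two attainable counts, 3/15 and 4/15, would make the range plain.
- **Section 10.2, exploratory test:** name the comparison as Arm A (the single high-dose RIF arm with LZD) against Arm B.
- **Synopsis, 4.0 and 4.1.7:** reconcile with the randomisation list actually used, stating whether HIV status was a stratum and whether LZD is allocated within RIF arm.
- **Section 10.2, CMH test:** state the strata as RIF dose by TBM grade (1 against 2–3). Keeping RIF dose suits the protocol's own hypothesis that "CSF and plasma LZD PK exposure parameters will be lower when administered with high dose compared with standard dose RIF".

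The cost is a sentence each in 10.1 and 10.2, plus the reconciliation. Grade is already recorded. Adding it costs about 1 point of power if it is not prognostic (largest simulated loss 1.3). Crossing in HIV status as well, for eight cells, should not be automatic: it cost 2.0 to 4.6 points at OR 1–2, with randomisation by grade and an assumed 70% HIV prevalence. No sample size, dose or data collection changes.

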Higher doses of RIF are well tolerated with a favorable safety profile. We will randomize participants to high (35 mg/kg) versus standard dose (10 mg/kg) oral RIF. The most common side effect of RIF is harmless red discoloration of bodily fluid (urine, tears and CSF). Other well-recognized side effects of RIF include gastrointestinal upset, rash, flu-like syndrome and thrombocytopenia. Drug-induced liver injury occurs in 20% HIV-infected patients on TB treatment. The drugs most commonly implicated are INH, PZA, and RIF. However, transaminitis is only seen in 0-2.5% of patients treated with RIF monotherapy, so INH and PZA are the most likely culprits. RIF oral doses as high as 40 mg/kg once daily for 14 days and doses of 35 mg/kg for up to 12 weeks have been safe and well-tolerated in clinical trials^{15,16}. In the ReDEFINE dose-finding study, oral RIF as high as 30 mg/kg daily (1350 mg) for 30 days were well tolerated without any increase in the incidence of adverse effects¹⁴.

Several linezolid characteristics favor its use as adjunctive therapy for TBM. Although RIF is the cornerstone of treatment of TBM, even with higher dosing to overcome poor CSF penetration, adjunctive therapies that enhance the potential benefit of high dose RIF may be needed to improve outcomes of TBM. Of new or repurposed drugs in the development pipeline for TB, many coming into clinical use (e.g., bedaquiline, delamanid) are highly protein bound and thus may not freely penetrate the BBB.^{7,17} Linezolid (LZD), a member of the oxazolidinone family with *in vitro* activity against TB,¹⁸⁻²² combines superb CNS penetration and excellent oral bioavailability.^{9,23-25} LZD has been included as salvage therapy for drug resistant (DR) TB.²⁶ In extensively DR (XDR) pulmonary TB, 89% receiving LZD achieved culture sterility by 6 months.²⁷ Acquired resistance was uncommon and occurred late, suggesting a high barrier to LZD resistance. Of 30 patients receiving 6 months of LZD 1200 mg, bedaquiline, and pretomanid for DR TB in the Nix-TB trial, 75% achieved culture sterility by 8 weeks.²⁸ Although LZD has largely been used for DR TB, it may also be valuable for drug susceptible TB. Few data are available on LZD use in TBM,²⁹ and none from randomized trials. In retrospective studies, LZD 600 mg BID in adults and 10 mg/kg every 8 hours for children was associated with better neurologic outcomes and lower mortality.^{30,31}

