7.6 Recording of AEs

The objective of the AE endpoint is to assess linezolid drug toxicity when administered with high and standard dose rifampicin among this critically ill population with high mortality. AEs grade 3-5 will be recorded via the AE recording CRF. The clinical course of each event should be followed until resolution, stabilization, or until it has been determined that the study treatment is not the cause. All unresolved AEs at study termination should be followed until the events are resolved, otherwise explained.

Asymptomatic laboratory abnormalities are not reportable AEs. However, abnormal laboratory results constitute an AE if the abnormality:

- is associated with a serious adverse event (e.g. death, hospitalization)
- is associated with clinical signs or symptoms
- leads to additional treatment or to further diagnostic tests, (other than repeat lab check), or
- is considered by the investigator to be of clinical significance

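### Minor: no planned analysis gives linezolid myelosuppression at each rifampicin dose, and the comparison within linezolid recipients cannot separate it from rifampicin's own effect

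*Combined protocol and SAP*

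**What the plan says.** Section 7.6 states the purpose: "The objective of the AE endpoint is to assess linezolid drug toxicity when administered with high and standard dose rifampicin". Section 10.2 defines the adverse event outcome as "Grade 3 or higher (yes/no) myelosuppression (e.g., anemia, thrombocytopenia, leukopenia) during the 4 weeks of therapy" and plans three analyses of it:

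1. Linezolid against no linezolid: "We will compare the frequency of myelosuppression between the LZD and no LZD arms across RIF dosing with the Cochran-Mantel-Haenszel test".
2. Rifampicin dose, restricted to linezolid recipients: "we will explore differences in the frequency of myelosuppression between the standard and two high dose RIF arms combined by a chi-square test".
3. A logistic exposure-response model to "test if the probability of myelosuppression and LZD discontinuation is related to PK measurements". The predictors listed are linezolid concentrations and AUC; no rifampicin term is listed.

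Section 10.1 concedes that the rifampicin-dose comparison among linezolid recipients may be underpowered. It does not mention the lack of a no-linezolid control for that comparison.

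The background (Section 1.0) bears on rifampicin's own effect in two ways. It says: "Other well-recognized side effects of RIF include gastrointestinal upset, rash, flu-like syndrome and thrombocytopenia". It also reports that about 30 mg/kg daily for 30 days was tolerated with no rise in adverse effects.

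**The concern.** Linezolid's toxicity at a given rifampicin dose is its excess over the matching arm without linezolid: A against C at high dose, B against D at standard dose. The factorial design randomises both controls. Only analysis 1 uses C and D, and it combines A-versus-C and B-versus-D into a single linezolid effect. Section 10.2 leaves it unclear whether its strata are rifampicin dose or the randomisation strata, but neither choice tests whether the effect differs by rifampicin dose. No interaction term, homogeneity test, dose-specific linezolid effect or C-versus-D comparison is planned.

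Analysis 2 is therefore the only analysis that bears on the question in Section 7.6. A and B differ in rifampicin dose as well as in any change in linezolid exposure that the dose causes. The protocol's hypothesis (Section 2.0) is lower linezolid exposure with high dose rifampicin, which would tend to lower A. Any direct effect of rifampicin on counts would raise A. If both were present, one could hide the other.

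**Working it through.** **Inputs.** Myelosuppression 40% with and 10% without linezolid, 30 against 30, significance level 0.05 (Section 10.1; two-sided assumed). Two successive 1:1 randomisations of 60 participants (Sections 3.0 and 4.1.7) give 60/4 = 15 per arm. The documents do not split the 10% by rifampicin dose, so every C/D split below is an assumption.

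**The plan's own figures.** Power for 40% against 10% with 30 per group, unpooled normal: SE = √[(0.24 + 0.09)/30] = 0.105; 0.30/0.105 − 1.96 = 0.90; power 81.6%. Exact enumeration of the uncorrected chi-square gives 79.6%, and a simulated Cochran-Mantel-Haenszel test with 15 per arm gives 79.9%. The stated 80% is reproduced under these uncorrected tests (Fisher's test gives 70.5%). The stated 90% interval for 25% of n=20 is also reproduced: Clopper-Pearson for 5/20 is 10.4% to 45.6%, half-width 17.6 points.

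**Group size.** Table 1 has one high dose rifampicin arm with linezolid, of about 15, and not two arms or 20 people. At 15 the same interval is 5.7% to 44.0% for 3 events and 9.7% to 51.1% for 4 events.

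**What A−B measures.** With A to D as event risks, the change in linezolid-attributable risk is (A−C) − (B−D). Subtracting:

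(A−B) − [(A−C) − (B−D)] = C − D.

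So A−B equals the change in linezolid toxicity only if rifampicin dose has no effect on the outcome without linezolid.

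**Masking.** Suppose linezolid's excess is 20 points with high and 40 with standard dose rifampicin (true change −20), keeping the plan's means of 40% and 10%. SE(A−B) = √{[A(1−A) + B(1−B)]/15}; the four-arm contrast adds the C and D terms. All entries are in % or points.

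| Assumed C / D | A / B | A−B | (A−C)−(B−D) | C−D | SE of A−B | SE of four-arm contrast |
|---|---|---|---|---|---|---|
| 10 / 10 | 30 / 50 | −20 | −20 | 0 | 17.5 | 20.7 |
| 12.5 / 7.5 | 32.5 / 47.5 | −15 | −20 | 5 | 17.7 | 20.8 |
| 15 / 5 | 35 / 45 | −10 | −20 | 10 | 17.8 | 20.8 |
| 20 / 0 | 40 / 40 | 0 | −20 | 20 | 17.9 | 20.7 |

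The last row is an extreme.

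**False signal.** Suppose linezolid's excess is 30 points at both doses (B 40%, D 10%) and rifampicin alone adds 15, 20 or 30 points. A−B is then 15, 20 or 30 points although linezolid toxicity is unchanged. In simulation the A-versus-B chi-square rejects in 12%, 18% or 37% of trials (4.8% with no rifampicin effect). The four-arm contrast averages about 0 and its Wald test rejects in about 6.4%.

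**Precision.** Half-width of the 95% interval for the four-arm contrast: 1.96 × 0.208 = 0.41, about ±40 points. With A 25%, B 55% and C = D = 10%, its SE is 0.202, so the difference detectable with 80% power is 2.80 × 0.202 = 57 points.

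**Scale.** If rifampicin multiplies the odds by 2 both with and without linezolid, the risks become A 57.1%, B 40%, C 18.2%, D 10%. The logistic interaction is zero, but the risk contrast is (57.1 − 18.2) − 30 = 9 points. With odds ratios of 3 and 4 it is 12 points. The two scales can disagree on whether linezolid toxicity changed.

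**The case against.** A reader might infer that the plan will report rifampicin's own effect as a change in linezolid toxicity, and that the linezolid dose recommendation would be distorted. The documents do not support that. Section 10.2 promises only to explore differences in frequency among linezolid recipients, and does not say the result will be attributed to linezolid. The stated dosing algorithm comes from simulation with the PK model, and exposure-driven toxicity is addressed by the exposure-response model. The formal secondary objectives and endpoints (Sections 2.3 and 2.4) do not list linezolid toxicity by rifampicin dose; that question appears in Section 7.6.

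A reader might also infer that the protocol expects more cytopenia with more rifampicin. It does not. Thrombocytopenia appears in a general side-effect list with no grade, rate or dose relation, and the dose-specific evidence cited in Section 1.0 is reassuring, although at about 30 and not specifically for Grade 3 or higher counts. Nor are C and D unused: they enter the Cochran-Mantel-Haenszel test.

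The strongest statistical objection is variance. As an estimate of the change in linezolid-attributable risk, A−B has a root mean squared error of √(0.0313 + 0.05²) = 0.184 at a 12.5/7.5% split, against 0.208 for the four-arm contrast. At 15/5% the figures are 0.204 and 0.208; at 20/0% they are 0.268 and 0.207. The four-arm contrast wins only when C−D exceeds about 11 points, and no document suggests a gap that large. This stands, and it is a reason not to drop A versus B. It is no reason to omit A−C and B−D, which are what Section 7.6 asks about. The conceded lack of power is a separate matter, since more participants would not remove the C−D term.

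**Conclusion.** The gap is real and minor. No analysis in Section 10.2 estimates linezolid toxicity at each rifampicin dose, and the within-linezolid comparison cannot stand in for it, because it differs from the wanted quantity by exactly C−D. That identity needs no assumption. The size does: the documents give no rifampicin-dose effect on blood counts, and 0 to 20 points reflects assumed splits of the planned 10%. A versus B remains a valid randomised comparison of regimens.

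The matter touches a secondary safety reading that the plan itself labels exploratory and concedes to be low in power. It does not touch the primary PK endpoint. Separately, the reference to two high dose arms and the n=20 in Section 10.1 do not fit the design in Table 1; A versus B is the only reading of the comparison that does.

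**What to change.** In Section 10.2:

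- Tabulate Grade 3 or higher myelosuppression in each of the four arms.
- Report the linezolid risk difference at each rifampicin dose (A−C and B−D) and their difference, with 95% confidence intervals, labelled exploratory. Name the risk-difference scale, and do not present a logistic interaction as equivalent.
- Keep A versus B, described as a comparison of regimens and not as linezolid toxicity by rifampicin dose.
- Reconcile the two high dose arms in Section 10.2 and the n=20 in Section 10.1 with the single high dose rifampicin plus linezolid arm of about 15 in Table 1.

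The cost is wording. The arms are already randomised, and the schedule of evaluations (Table 5) has haematology at screening, entry and weeks 1, 2 and 4 without distinction by arm. The drawback is imprecision: an SE of about 0.21 against 0.18 for A−B. The added contrast is for estimation only and does not restore power.
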